1. SYNOPSIS

Study Title	Optimum radiographic assessment of the medial and lateral tibiofemoral compartments within the arthritic knee
Short title	Optimum radiographic assessment of the knee
Study Design	Clinical Investigation
Study Participants	Patients aged over 50 years with knee osteoarthritis, any grade, affecting the tibiofemoral joint.
Planned Sample Size	225
Planned Study Period	August 2015 to January 2017 (18 months)
	Objectives
Primary	To assess the accuracy of different xray views of measuring joint space width within each compartment within the knee.
Secondary	
To define the sensitivity and specificity of four different xray views at predicting bone on bone arthritis and joint space narrowing within each of the knee compartments and suitability for unicompartmental knee replacement.
 
To define the sensitivity and specificity of MRI at predicting suitability for unicompartmental knee replacement.
 
To assess the sensitivity and specificity of different xray techniques at inferring the status of soft tissue structures (anterior cruciate ligament and medial collateral ligament) within the arthritic knee.
 
To develop a decision aid to help clinicians decide between likelihood of a patient being a candidate for unicompartmental knee replacement based on pre-operative xray and MRI findings.

2. ABBREVIATIONS

CI	Chief Investigator
CRF	Case Report Form
CTRG	Clinical Trials & Research Governance, University of Oxford
GCP	Good Clinical Practice
GP	General Practitioner
MRI	Magnetic Resonance Imaging
ICF	Informed Consent Form
NHS	National Health Service
NRES	National Research Ethics Service
OA	Osteoarthritis
PI	Principal Investigator
PIL	Participant/ Patient Information Leaflet
R&D	NHS Trust R&D Department
REC	Research Ethics Committee
SOP	Standard Operating Procedure
TKR	Total Knee Replacement
UKR	Unicompartmental Knee Replacement

3. BACKGROUND AND RATIONALE

Xrays are the most frequently used imaging test when evaluating the knee for joint replacement. They are non-invasive, safe and cost effective. They allow assessment of: progression of disease, appropriateness for joint replacement (in particular UKR) as well as likely prognosis following replacement. Despite a multitude of standardised views there is a lack of consensus regarding the optimum views to evaluate joint space narrowing within each compartment (lateral, medial and patellofemoral).

The optimum imaging protocol is one that is acceptable to patients, involves the fewest xrays to obtain the most clinically relevant information and one that utilises the least resources in terms of staff and equipment. Currently standard assessment involves: standing anteroposterior, lateral and skyline views. In addition in patients being considered for joint replacement valgus/versus stress xrays are used to evaluate the lateral compartment (as well as medial collateral ligament) and medial compartment respectively to assess the status of the cartilage. In patients with loss of cartilage on one side, typically medial, but preserved cartilage on the other a UKR, as opposed to TKR, may be indicated.

Currently there is a lack of consensus amongst orthopaedic surgeons in the UK as to the best way to image the knee joint to establish degree and pattern of arthritis [1, 2]. For a long time it has been known that weight bearing views are a better method at establishing the true joint space compared to non-weight bearing views width due to the increased forces across the joint [3-5]. In addition it is known that full extension views, despite being the most commonly used view, may also underestimate joint space

narrowing as in full extension the femur and tibia articulate across an area of the joint that is not typically involved during activity, and hence can have relatively well preserved cartilage, giving a false impression of the joints disease state[6]. These findings have been adopted, and continue to be adopted, into routine clinical practice and there continues to be an increase in the proportion of surgeons performing standing and semi-flexed views [2]. However the best method of evaluating the disease state in each compartment has yet to be defined.

When deciding between UKR and TKR the detection of the degree and pattern of arthritis is of critical importance. UKR are known to perform poorly in partial thickness disease and require full thickness cartilage in the retained tibiofemoral compartment[7, 8]. To establish whether a patient meets the indications for UKR x-rays are used with stress views being the gold standard, as well as the standard assessment that the studies of long term outcomes on UKR are based. Gibson and Goodfellow, who were first to describe stress x-rays in the workup of a patient for UKR, reported that those patients with a joint space width of more than 5mm in the lateral compartment had intact lateral cartilage during surgery making them appropriate for UKR [9]. More recently Waldstein *et al.* reported that patients with a lateral joint space width of more than 4mm may be appropriate for UKR however overall they noted poor correlation between joint space width measured on valgus stress views and intra-operative Outerbridge grade[10].

In addition to the low quantity of evidence regarding the relationship between stress views and intra-operative status of the joint the feasibility of performing stress x-rays also limits their use. Stress x-rays are resource dependent, can be uncomfortable for patients and require an additional practitioner. As such they are often not performed with many clinicians adopting alternative x-ray views, MRI or direct observation via arthroscopy [11]. It has been proposed that standing views with the knee in 15 degrees then 45 degrees flexion may load the medial and lateral compartments respectively and that these views may be an alternative to stress views without the requirement for an additional practitioner. However the outcomes based on these forms of assessment, and the relationship between the joint space width measured using these contemporary techniques has not been reported. An alternative would include a stress device that allows a stress x-ray to be performed without the requirement of the clinician.

This study will evaluate the status of knee cartilage in 225 patients with varying degrees, and patterns, of knee OA using standing extension anteroposterior, 15 degrees flexion posteroanterior, 45 degrees flexion posteroanterior and valgus and varus stress views as well as MRI. These results will be compared to the gold standard imaging technique of stress views as well as to direct measurements of retrieved tissue in those patients who undergo knee replacement surgery. The sensitivity and specificity of each of the imaging techniques at predicting suitability for UKR will be calculated, the optimum imaging views proposed, and ultimately the results of this study will be used to develop a decision aid, based on optimum views, to help clinicians decide between likelihood of a patient being a candidate for UKR based on pre-operative x-ray and MRI findings.

4. OBJECTIVES AND OUTCOME MEASURES/ENDPOINTS

Objectives	Outcome Measures
Primary Objective 
 • To assess the accuracy of different xray views of measuring joint space width within each compartment within the knee. 	Joint space width in the medial and lateral tibiofemoral compartments of the knee measured in mm.
Secondary Objectives 
 • To define the sensitivity and specificity of four different xray views at predicting bone on bone arthritis and joint space narrowing within each of the knee compartments and suitability for UKR. • To define the sensitivity and specificity of MRI at predicting suitability for UKR. • To assess the sensitivity and specificity of different xray techniques at inferring the status of soft tissue structures (anterior cruciate ligament and medial collateral ligament) within the arthritic knee. 	
A joint space width of 0mm will be classified as bone on bone arthritis, >0mm to <5mm will be classified as joint space narrowing and $\geq 5\text{mm}$ will be classified as full thickness cartilage. The sensitivity and specificity of each technique, at detecting each disease state in each compartment, compared to the gold standard of stress views will be recorded.
 
The sensitivity and specificity of MRI, compared to the gold standard of stress views, at predicting the status of each compartment will be recorded.
 
In patients proceeding to joint replacement as part of their standard clinical pathway the sensitivity and specificity of different xray techniques at inferring the status of soft tissue structures (anterior cruciate ligament and medial collateral ligament) within the arthritic knee will be compared to operative findings.

Tertiary Objectives 
 • To develop a decision aid to help clinicians decide between likelihood of a patient being a candidate for UKR based on pre-operative xray and MRI findings. 	The findings from this study will be used to develop a decision aid. The sensitivity and specificity of this decision aid will be calculated in the cohort of patients undergoing surgery using intra-operative audit findings as the gold standard.

5. STUDY DESIGN

The study is a clinical investigation to determine the optimum xray technique for each compartment of the knee in patients aged over 50 years with knee arthritis.

All patients attending knee clinic will be informed about the study in advance. Those patients who meet the inclusion criteria will be referred to the research team in clinic. Screening would be performed in clinic and in those patients that do not have exclusion criteria further information about the study will be given and if the patients agree to participation valid informed consent will be taken. Screening and consent would take around 10 minutes. Two additional xray views will be taken alongside routine clinical views and would be expected to take a maximum of 10 additional minutes. An MRI scan would also be arranged, and this would take place at a separate time arranged at the patients convenience and would take around 30 minutes. No further research appointments would be performed. In patients who, as part of their clinical care, undergo knee replacement the excised joint surfaces, which are normally disposed of, would be retained and the degree and pattern of articular cartilage wear would be quantitatively evaluated before disposal. In addition an audit of the intra-operative findings would be performed.

Evaluation for inclusion and exclusion criteria would be via pre-tested standardised pro forma. A pain visual analogue scale would be used to assess for the presence and degree of pain during stress views. Xray images would be measured using custom measuring software (Matlab, Massachusetts , USA), MRI images would be measured using a segmentation method that has previously been described (Solidworks, Massachusetts , USA). Intra-operative audit of joint surfaces and soft tissue structures would be recorded on a standardised, pre-tested pro forma. Retrieved intra-operative samples of the joint surface would be scored using a validated technique, digitally photographed and surface geometry measured using a 3D laser scanner.

A flow chart of the study can be seen in Appendix A.

6. PARTICIPANT IDENTIFICATION

6.1. Study Participants

Patients aged over 50 years referred to knee clinic with radiographic evidence of knee osteoarthritis, any grade, affecting the tibiofemoral joint

6.2. Inclusion Criteria

- Participant is willing and able to give informed consent for participation in the study.
- Male or Female, aged 50 years or above.
- Knee osteoarthritis any grade, affecting the tibiofemoral joint
- In the Investigator's opinion, is able and willing to comply with all trial requirements.
- Willing to allow his or her General Practitioner and consultant, if appropriate, to be notified of participation in the trial.

6.3. Exclusion Criteria

The participant may not enter the study if ANY of the following apply:

- Previous joint replacement on ipsilateral knee
- Previous anterior cruciate ligament reconstruction or injury
- Previous high tibial osteotomy
- Previous intraarticular fracture
- History of Inflammatory arthritis
- Unable to stand with assistance for two minutes

7. STUDY PROCEDURES

- Screening and consent (performed at clinic appointment) - 10 minutes
- Standard Clinical Xrays
 - Standing anteroposterior view
 - Lateral view
 - Patellofemoral view
 - Valgus stress view (clinician performed or using validated device)
 - Varus stress view (clinician performed or using validated device)
- Research xrays (performed at the same time as routine clinical xrays) – 10 minutes
 - Standing posteroanterior (PA) view 15 degrees flexion
 - Standing posteroanterior (PA) view 45 degrees flexion
- MRI (performed during a separate appointment at the patients convenience) – 30 minutes
- Measuring of routinely retrieved joint surface cartilage (performed in research laboratory)

7.1. Recruitment

All patients attending knee clinic will be provided with an information leaflet via the post 2 weeks before their appointment about the study. Patients will be identified as eligible by the clinical team and will be referred to the research team who will be based in clinic. The research team will screen patients using a standardised, pre-tested, pro forma. Further information about the trial will be provided. Patients who meet inclusion, but not exclusion criteria, and who are willing to participate in the study will be consented for the study.

7.2. Informed Consent

Consent will be performed by a member of the research team who is suitably qualified and experienced, and has been authorised to do so by the Chief Investigator.

Written and verbal versions of the Participant Information and Informed Consent will be presented to the participants detailing no less than: the exact nature of the study; what it will involve for the participant; the implications and constraints of the protocol; the known side effects and any risks involved in taking part. It will be clearly stated that the participant is free to withdraw from the study at any time for any reason without prejudice to future care, and with no obligation to give the reason for withdrawal.

The participant will be allowed as much time as wished to consider the information, and the opportunity to question the Investigator, their GP or other independent parties to decide whether they will participate

in the study. The patient must personally sign and date the latest approved version of the Informed Consent form before any study specific procedures are performed. The written Informed Consent will then be dated and signature of the person who presented and obtained the Informed Consent. A copy of the signed Informed Consent will be given to the participant. The original signed form will be retained at the study site. One copy will be filed in the patient's medical notes.

7.3. Screening and Eligibility Assessment

Screening will be performed via pre-tested, standardised, pro forma by a member of the research team. A maximum period of 2 months will be permitted between screening and MRI. Analysis of excised joint surfaces in those patients who undergo knee replacement as part of their clinical management will only be considered valid if the replacement is performed within 6 months of screening.

7.4. Baseline Assessments

At baseline a patient name, gender and date of birth will be recorded, together with hospital and NHS number will be recorded on the patient data sheet which will be linked to the CRF by way of a study number.

Research xray views will also be performed during the baseline assessment. In addition to routine clinical xrays: standing anteroposterior, lateral, skyline views and valgus/varus stress xrays two research xray views will be performed.

These two views are with the patient standing, hands resting on a frame for stability. The xrays are taken in the postero-anterior direction. The first of these standing views is taken with the knees flexed to 15 degrees, the second with the knees flexed to 45 degrees.

7.5. Subsequent Visits

One further appointment would be required for this study. This appointment would be for MRI of the knee. The appointment would be performed at the patient's convenience and would take 30 minutes in total. No further appointments would be required for the patient as part of this research project.

7.6. Discontinuation/Withdrawal of Participants from Study

Each participant has the right to withdraw from the study at any time. In addition, the Investigator may discontinue a participant from the study at any time if the Investigator considers it necessary for any reason including:

- Pregnancy
- Ineligibility (either arising during the study or retrospectively having been overlooked at screening)
- Significant protocol deviation
- Withdrawal of Consent

In the event of patient withdrawal from the study analysis of data obtained prior to withdrawal will be analysed as part of the study.

Withdrawn participants will not be replaced.

The reason for withdrawal will be recorded in the CRF.

7.7. Definition of End of Study

The end of study is 6 months following recruitment of the last patient.

8. INTERVENTIONS

In addition to the standard clinical imaging protocol described above trial participants will undergo:

- 15 degrees flexion postero-anterior view
- 45 degrees flexion postero-anterior view
- MRI knee without contrast

In those patients undergoing surgery as part of their routine clinical management:

- Intra-operative audit of joint surface and status of ligaments within the knee
- Assessment of retrieved samples of joint surface that would otherwise be disposed of

9. SAFETY REPORTING

The study is low risk however in the event of an adverse event (AE) or serious adverse event (SAE) occurring to a participant this would be reported to the REC and R&D.

10. STATISTICS AND ANALYSIS

10.1. Description of Statistical Methods

Joint space width of each of the compartments will be measured on each routine and research xray views taken using a standardised technique using custom software (Matlab, Massachusetts, USA). To compare the accuracy and agreement of different radiological views at measuring joint space width statistical methods for assessing agreement between two methods of clinical measurement as described by Bland and Altman will be used with stress views defined as the gold standard for comparison [12, 13].

For the secondary outcomes each of the compartments on each of the xray views will be classified as demonstrating bone on bone arthritis, full thickness cartilage or narrowing of joint space width. The sensitivity and specificity of each of the views at predicting each of these disease states will be compared with stress views which will be defined as the gold standard. The sensitivity and specificity of each of the views at predicting suitability for UKR will be calculated based on pre-defined indications of UKR.

The sensitivity and specificity of MRI at predicting suitability for UKR, based on pre-defined xray derived indications as the gold standard will be calculated.

The sensitivity and specificity of different xray techniques at inferring the status of soft tissue structures (anterior cruciate ligament and medial collateral ligament) within the arthritic knee will be evaluated against both MRI and intra-operative findings.

A decision aid will be developed based on the findings of this research and the sensitivity and specificity of this decision aid at predicting suitability for UKR will be calculated. Further work will then be performed to validate this scoring system.

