10.2. The Number of Participants

From two previous studies evaluating the utility of PA views in 15 degrees flexion compared with AP standing for long term evaluation of progression of knee arthritis the difference in mean joint space width measured on Lyon Schuss and AP standing views is between 0.63mm with a population standard deviation of 1.1. This gives an effect size of 0.57. At a power of 0.8 and significance level of 0.05 using the Altman nomogram the required sample size would be 100 patients. From audit it has been identified that 50% of patient from clinic will be treated with surgery. In addition to allow for errors in xray alignment making interpretation not valid an additional 25 patients will be added giving a sample size of 225 patients.

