10.3. Analysis of Outcome Measures/Endpoints

Each image will be measured independently and statistical analysis will be performed blinded to the treatment outcome. Should a patient withdraw consent prior to termination of the study data that has been collected will only be used for analysis where, for each endpoint, a complete set of data is present.

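### Does the primary agreement analysis need a written rule for joint space widths at or near 0 mm?

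*Combined protocol and SAP*

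**What the plan says.** The primary objective (section 4) is the accuracy of the X-ray views in measuring joint space width in mm, for the medial and lateral tibiofemoral compartments. Its analysis is one sentence in section 10.1: "statistical methods for assessing agreement between two methods of clinical measurement as described by Bland and Altman will be used". The same sentence fixes the reference: "with stress views defined as the gold standard for comparison". Two method papers are cited. No form of limits, scale or treatment of zero readings is named.

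Zero readings are to be expected. Section 6.2 admits "Knee osteoarthritis any grade, affecting the tibiofemoral joint", and section 4 makes the floor a disease state of its own: "A joint space width of 0mm will be classified as bone on bone arthritis". That classification serves the secondary sensitivity and specificity outcomes. Section 3 describes candidates for unicompartmental replacement as having "loss of cartilage on one side, typically medial, but preserved cartilage on the other". Section 5 gives the aim as "to determine the optimum xray technique for each compartment of the knee".

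Section 10.3 adds that "statistical analysis will be performed blinded to the treatment outcome". Section 11.2 has images measured in duplicate by an evaluator who is blind to the patient's other images and to the final treatment. Neither section mentions the floor.

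**The concern.** Joint space width cannot be negative. When both readings are near 0 mm their difference must also be near 0, so on a plot of difference against average the spread closes up at the left-hand end. A single bias and a single SD for all knees would then misdescribe both ends: limits too wide near the floor and, in many settings, too narrow above it.

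If an analyst pooled all knees under constant limits, the result would depend partly on how many knees sit at the floor. Cartilage loss is typically medial, so that share may differ between compartments, and one view could show different limits medially and laterally partly through case mix. The stated blinding of the analysis covers treatment outcome and not the view, so a choice of limits made after seeing the data could be made knowing which view it favours. This is the primary analysis, which is why a one-sentence specification draws attention.

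**Working it through.** **The plan's own figures.** Section 10.2 describes the joint space width difference "measured on Lyon Schuss and AP standing views is between 0.63mm with a population standard deviation of 1.1". The effect size is 0.63/1.1 = 0.57. With two-sided 5% significance and 80% power, n per group = 2 × (1.96 + 0.84)² / 0.57² ≈ 48.3, so 49 per group and 98 in total. This agrees with the plan's 100, and 100/0.5 + 25 = 225. None of this depends on how 0 mm readings are handled.

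**The bound.** Let V and S be the readings on the view and on stress, D = V − S and A = (V + S)/2. Since V, S ≥ 0, |D| ≤ 2A. At any level A, therefore, bias² + SD² ≤ 4A².

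Inputs: bias 0.63 mm and SD 1.1 mm from section 10.2. Using them as bias and SD of differences is an assumption: 1.1 is called a population SD, and the comparison there is not against stress views.

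- Constant limits: 0.63 ± 1.96 × 1.1 = −1.53 to 2.79 mm.
- Lower limit out of reach when 2A < 1.526, that is A < 0.76 mm.
- Upper limit out of reach when 2A < 2.786, that is A < 1.39 mm.
- This bias and SD cannot both hold when A < √(0.63² + 1.1²)/2 = 0.63 mm.
- With SD from 0.5 to 1.5 mm the three points become 0.17-1.16, 0.80-1.78 and 0.40-0.81 mm.

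A constant bias of exactly zero is compatible with the bound. Only a constant SD or a constant non-zero bias is excluded.

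**What pooled constant limits would do.** This is a simulation under assumptions, since the documents give neither the floor share nor the width distribution. Floor shares were 5, 20 and 40%, with other knees uniform on 0-6 mm. Bias was 0 or 0.63 mm and SD of differences 0.7, 1.1 or 1.5 mm. Four patterns of reading at the floor were used: the same error as other knees, exactly 0 on both views, or stress 0 with the view centred on 1.0 or on 1.5 mm. That makes 3 × 2 × 3 × 4 = 72 cases.

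| Floor share | Constant limits, knees averaging ≥ 1 mm | Straight-line regression limits, same knees |
|---|---|---|
| 5% | 93-95% | 92-95% |
| 20% | 90-94% | 89-94% |
| 40% | 84-92% | 86-94% |

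Knees averaging below 1 mm are covered 95-100% by constant limits. Over all knees together, constant limits cover about 92-95% in every case.

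Moving from a 5% to a 40% floor share makes the limits 7-21% narrower if floor knees read 0 on both views or with ordinary error. If the view misses the loss by 1.0-1.5 mm, the change runs from 10% narrower to 44% wider. The direction is therefore not known.

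**What the alternatives cost.** Bands of the average restore about 95% coverage at 1 mm or more but hold fewer knees. The confidence half-width on a limit is 1.96 × SD × √(1/n + 1.96²/(2(n − 1))). At SD 1.1 mm this gives 0.26 mm with 200 knees, 0.37 mm with 100 and 0.48 mm with 60.

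**The case for a change.** The best case for a written rule is that this is the primary analysis, the mechanism is arithmetic and not conjecture, and a rule would cost only wording. The contents of the cited method papers are not in the documents, so the citation cannot be taken as settling which form of limits will be used. A different model (latent normal widths with SD 2 mm, floored at 0, with 10, 30 and 50% of reference readings at 0) shows the same pattern. There, 5.7, 10.4 and 18.1% of knees averaging 3-5 mm fall outside nominal 95% limits.

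Two things stand: section 10.1 is silent on the floor, and a constant SD cannot hold there. The rest does not carry a change.

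- Every coverage and width figure assumes pooled constant limits, which the plan does not adopt.
- No comparison of medial with lateral limits is planned. Views are compared within a compartment on the same knees, which is less exposed to case mix. Where a view reads 1.0-1.5 mm on knees with a stress reading of 0, wider limits reflect disagreement that the study sets out to find.
- The blinding argument is weak, because a view-by-view agreement analysis has to identify the view. The readings themselves are protected by section 11.2.
- The obvious remedies are not clearly better. Switching to level-dependent limits only if a trend is seen, with no threshold or cut-points, leaves the same choice until after the data are seen. Straight-line regression limits do no better than constant ones at a 20% floor share. Bands cost precision.

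**Conclusion.** No change is needed. This is a gap in detail that a competent analyst fills in the ordinary course of the work. Differences are plotted against the average of the two readings, a closing spread near 0 mm shows on the plot, and the limits are reported accordingly. Counts of knees at 0 mm on one view and on both, by compartment, would be a natural addition to the report, but the plan does not depend on saying so.

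The possible effect runs from negligible (93-95% coverage above 1 mm at a 5% floor share) to moderate (84-92% at 40%), and arises only if constant limits are pooled over all knees. These figures rest on assumed floor shares, an assumed width distribution, and SDs of differences from 0.7 to 1.5 mm, none of which the documents supply for comparison with stress views. No planned conclusion is shown to change: the within-compartment comparison of views is little exposed, and sensitivity and specificity, including bone-on-bone detection and suitability for unicompartmental replacement, do not use the limits.

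### Section 10.1 sets each view against a reference and never estimates a difference between views, and the power in Section 10.2 belongs to a comparison that no analysis section lists

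*Combined protocol and SAP*

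**What the plan says.** **Aim.** Section 3 says that the work will end with "the optimum imaging views proposed" and with a decision aid built on them. Section 5 describes the study as finding the best x-ray technique for each knee compartment.

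**Analysis.** Section 10.1 announces a comparison of accuracy and agreement between views. The method it names is two-method agreement, which "will be used with stress views defined as the gold standard for comparison". The other analyses have the same form, one technique against a reference:
- disease state on each view, against stress views;
- MRI, against x-ray-derived indications for unicompartmental replacement;
- ligament status on x-ray, against MRI and operative findings;
- the decision aid, against the intra-operative audit (Section 4).

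Section 3 adds retrieved tissue as a further reference. Sections 4, 10.1 and 10.3 give no contrast between views, no interval for such a contrast and no statistical criterion for preferring one view.

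**Size.** Section 10.2 starts from a between-view contrast: "the difference in mean joint space width measured on Lyon Schuss and AP standing views is between 0.63mm", "with a population standard deviation of 1.1". It continues "This gives an effect size of 0.57" and "At a power of 0.8 and significance level of 0.05 using the Altman nomogram", "the required sample size would be 100 patients". This is doubled because "50% of patient from clinic will be treated with surgery", and 25 are added for unreadable films, giving 225.

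**Design.** Sections 7 and 7.4 give each participant the standing AP, both flexed PA views and both stress views.

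**The concern.** Proposing the optimum views needs a statement about how the views differ from one another. Separate bias, limits of agreement, sensitivity and specificity for each view do not supply it. Two views read on the same knee have correlated errors, so their separate results cannot show whether a gap between them is larger than chance. A reader of the final report would see several accuracy figures side by side with nothing to say which gaps are real.

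The stated power has a related problem. It is calculated for 15-degree PA against AP, a contrast that no analysis section contains, and with a formula for separate groups of patients. It therefore supports neither the agreement analysis against stress views nor any ranking of views.

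**Working it through.** **1. Reproducing the figure in Section 10.2.** Inputs from the plan: difference 0.63 mm, SD 1.1, power 0.80, significance level 0.05 (two-sided assumed).
- Effect size: 0.63/1.1 = 0.573, stated as 0.57.
- Two independent groups: n per group = 2(1.960 + 0.842)²/0.57² = 48.3, so 49 per group and 98 in total. The t-based version gives 50 per group, 100 in total.
- One-sided: 78 in total. Paired, with 1.1 taken as the SD of within-knee differences: 25.
- Inflation: 100/0.5 = 200, and 200 + 25 = 225.

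The 100 is thus correct for its own inputs, as the total for two independent groups.

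**2. The same contrast, paired.** The plan gives no SD of within-knee differences, so the correlation r between views is an assumption.
- SD of differences = 1.1 × √(2(1 − r)). This is 0.852 mm at r = 0.7 and 1.302 mm at r = 0.3.
- Smallest mean difference detectable at 80% power = 2.80 × SD of differences/√n.

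| Patients | r = 0.7 | r = 0.3 |
|---|---|---|
| 100 | 0.24 mm | 0.36 mm |
| 200 | 0.17 mm | 0.26 mm |

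To detect 0.63 mm, a paired analysis needs 48 patients at r = 0, 24 at r = 0.5 and 5 at r = 0.9. The planned size is ample for this quantity.

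**3. Link to the planned agreement analysis.** Let A, P and S be the widths on AP, 15-degree PA and stress views of one knee. Then (A − S) − (P − S) = A − P. The paired difference in Bland–Altman bias therefore equals the paired difference in mean joint space width, so step 2 applies to it directly.

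**4. Sensitivity and specificity.** Knees needed for a paired (McNemar) comparison of two views, with difference d and discordant proportion ψ: n = [1.960√ψ + 0.842√(ψ − d²)]²/d². For d = 0.10 and ψ = 0.15: (0.759 + 0.315)²/0.01, so 116. The plan gives no discordance rate; 15–30% is assumed.

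| Difference | Reference-positive knees, two-sided 0.05 | Bonferroni for three pairs (0.0167) |
|---|---|---|
| 5 points | 469–940 | 626–1,254 |
| 10 points | 116–234 | 155–312 |
| 15 points | 50–103 | 67–137 |

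The plan does not say how many knees will be reference-positive in each state and compartment.

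**5. How far equal views can separate by chance.** Simulation of three views with identical true sensitivity (assumed 80–90%, latent correlation 0 or 0.5):

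| Reference-positive knees | Best-to-worst gap of 5 points or more |
|---|---|
| 50 | 59–81% of studies |
| 100 | 43–71% |
| 200 | 16–46% |

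If instead one view is truly better (90% against 85% and 85%, correlation 0.5), it comes out strictly top in 63%, 79% and 91% of studies with 50, 100 and 200 positives.

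**6. Multiplicity.** Three pairs, two compartments and seven measures (absolute error, plus sensitivity and specificity for three disease states) give 3 × 2 × 7 = 42 possible intervals. Even three independent tests at 5% give 1 − 0.95³ = 14% chance of at least one false difference.

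**The case against.** The strongest defence is that the objectives in Section 4 ask for the accuracy, sensitivity and specificity of each view, and the planned analyses give exactly that. Section 3 asks whether flexed standing views could replace stress views. That is a question of view against stress view, and Bland–Altman agreement, which is itself computed within the knee, addresses it. This stands: the primary analysis is not invalid. It does not cover the step from separate accuracies to a proposal of optimum views, which Sections 3 and 5 also promise.

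Three stronger readings are tempting, and the documents do not support them.
- A reader might infer that every analysis uses stress views as reference. It does not: MRI, operative findings and retrieved tissue also serve. Each is still one technique against a reference, so the gap between views remains.
- A reader might infer that the view with the best point estimate will be declared optimum, and so chosen by chance. No such rule is written. Section 3 describes the best protocol partly by patient acceptability, number of x-rays and resources, and step 5 shows that a truly better view often comes out on top.
- A reader might infer that the planned size supports all paired comparisons because 0.17–0.26 mm is detectable. That figure is for mean joint space width only; step 4 shows much weaker support for sensitivity and specificity.

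**Conclusion.** The point holds in this form. Section 10.1 contains no estimate of any difference between index views, so the plan has no means of separating real from chance differences in accuracy. The 80% power in Section 10.2 attaches to no listed analysis and is calculated without the pairing that the design provides. The sample-size arithmetic is not wrong, and the number of patients is not shown to be too small for a paired mean difference.

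The absence of a planned contrast is read directly from the documents. Its practical size rests on assumptions: within-knee correlation, discordance, true sensitivity and number of reference-positive knees are not in the plan. Under the ranges used, 5-point gaps between equally sensitive views are common at 50–100 positives and still occur in 16–46% of studies at 200.

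**What to change.** 1. **Add paired contrasts to Section 10.1**, for each compartment, among AP, 15-degree PA and 45-degree PA. Name AP versus 15-degree PA as primary, on the paired difference in bias against stress views, and say whether the 5% level applies to each compartment or is split between the two. Make secondary the other pairs, the paired difference in absolute error (patient-level bootstrap interval) and the paired differences in sensitivity and specificity (McNemar-type intervals). Adjust these for multiplicity or label them exploratory.
2. **State the rule for claims.** Say that one view is more accurate than another only where the relevant adjusted paired interval supports it; otherwise report the views as not distinguished. Read a difference in signed bias together with each view's own bias and the absolute error, since biases of opposite sign can differ without either view being closer to the reference. Apply the acceptability and resource criteria of Section 3 as a separate, declared step when proposing the optimum views.
3. **Restate Section 10.2** for the paired AP versus 15-degree PA mean difference. Give the assumed within-knee correlation and the detectable differences for 100 and 200 patients. State that this power does not extend to sensitivity and specificity, and give the number of reference-positive knees expected.

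The cost is analysis text and a few lines of code in the Stata package already named, with no additional data. The price in results is that some views, especially on sensitivity and specificity, will probably have to be reported as not distinguished.
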